6.5.2. Pharmacokinetic Analysis

Pharmacokinetic analysis for Part 2 will be carried out in the same manner as described in [Section 6.2.1](#)

CCI
[REDACTED]

6.7. Subset Analyses

There are no planned subset analyses.

6.8. Baseline and Other Summaries and Analyses

6.8.1. Baseline Summaries

Baseline characteristics will be summarized and/or listed in participant level data listings:

- Demographics: will be summarized by dose level (Part 1) and overall across all dose levels, or by arm (Part 2). This will be based on the Full analysis set. Demographic data will also be listed in a data listing.
- Primary diagnosis: will be listed for all enrolled participants.
- Baseline signs and symptoms: will be summarized by dose level (Part 1) or by arm (Part 2) using the full analysis set. This data will also be listed for all enrolled participants.
- ECOG performance status: will be summarized by dose level (Part 1) or by arm (Part 2) using the full analysis set.

Prior medication, medical history, physical examinations will not be summarized or listed, unless it's deemed necessary.

6.8.2. Study Conduct and Participant Disposition

An accounting of the study participants will be tabulated. The participant dose level cohort will be listed. The Full Analysis Set will be used.

Participant discontinuation from treatment and study will be tabulated and listed for each participant separately with their reason for discontinuation. The Safety Analysis Set will be used.

6.8.3. Study Treatment Exposure

The Safety Analysis Set will be used for the analysis of treatment exposure.

Treatment exposure will be assessed with the following approaches:

- **Duration of Treatment (DOT):** defined as the last active dose date minus the first active dose date + 1. DOT will be summarized, as a continuous variable, by dose level for Part 1 and overall across all dose levels; or by arm for Part 2. DOT may also be categorized into different intervals (≥ 1 cycle; ≥ 2 cycles; ≥ 3 cycles etc.). Frequency and percentage of participants for each interval may be descriptively summarized by dose level for Part 1 and overall across all dose levels; or by arm for Part 2. DOT, when it is derived at participant level, will be derived for PF-07265028 and sasanlimab separately.
- **Treatment Compliance:** defined as the proportion of cumulative actually taken dose over the cumulative planned dose for cycle 1 (for the purpose of defining the per-protocol population for the MTD evaluation) and over the entire treatment period (i.e. between the first active dose date and the last active dose date). Treatment compliance will be calculated for PF-07265028 and sasanlimab separately.
- **Dose interruption** will be listed, reasons for dose interruption (e.g. AE), if available, will be included in the listing. Dose interruption is defined as a situation when the actual dose was adjusted from the planned dose (as collected in the case report form).
- **Listing by participant level of dosing administration data:** cycle number, start date and stop date of dosing period within each cycle (including records with 0 mg), total daily dose received for each dosing period, any missed doses with unknown dates (yes/no), number of missed doses with unknown dates, reason for any dosing changes, total planned dose, total actual dose received, percentage of planned dose, dose reduction (yes/no), and dose interruption (yes/no).

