In monotherapy, starting dose for PF-07265028 is 25 mg administered orally QD on a continuous basis. BLRM is used for dose finding until reaching MTD. Continuous BID dosing may be explored. The potential switch from continuous QD dosing to BID dosing would be based on emerging PK, PD and safety data. This switch may be needed if data demonstrate that PF-07265028 has a shorter than expected half-life with inadequate PK/PD coverage through QD dosing, or there are AEs related to C_{max} which might be mitigated by a lower dose given BID.

PF-07265028 will initially be administered under the empty stomach condition. The effect of food on PF-07265028 PK will be evaluated in at least 6 participants (food effect subset) at a dose level not exceeding the PF-07265028 MTD and RDE, either as a cohort in Part 1A or in 1 of the Part 2 cohorts. If emerging PK data from the food effect assessment suggest the effect of food on PF-07265028 PK is not clinically meaningful, participants may be instructed to take PF-07265028 without regards to food. In addition, the study has included a plan to assess the effect of food intake on tolerability and safety, if treatment-related Grade ≥ 2 GI toxicity is observed in $\geq 30\%$ participants with a minimum of 6 participants enrolled in total across all dose levels. The dose of PF-07265028 for the evaluation of food effect on tolerability is expected to yield a steady-state AUC and C_{max} not exceeding the AUC and C_{max} of PF-07265028 at the MTD administered under the empty stomach condition. If food intake could allow participants to tolerate the same or higher systemic exposure of PF-07265028 compared to the empty stomach condition, subsequent parts of the study will continue with the dosing regimen of PF-07265028 administered with food.

In combination therapy, sasanlimab 300 mg SC Q4W will be administered at the clinic together with oral administration of PF-07265028.

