6.1.1. Administration

6.1.1.1. PF-07265028

Participants will swallow PF-07265028 tablets whole with at least 8 ounces (240 mL) of water, and will not manipulate or chew the study intervention prior to swallowing. PF-07265028 will initially be administered QD by mouth for all cohorts on a continuous basis. Participants who are unable to swallow whole tablets may dissolve their dose in oral syringe(s) as outlined in the IP manual to allow for suspension administration either orally or via an NG tube. If supported by emerging data, BID continuous regimen may be considered. A cycle is defined as 28 days, regardless of missed doses or dose delays.

Participants will take PF-07265028 at approximately the same time within each dosing interval (ie, ± 3 hours of nominal time). On site visit days, participants will take the drug at the site after performing predose assessment. On other days, participants will be instructed to self-administer the drug at home. A dosing diary will be given to each participant to support at home dosing. The participants will be requested to note the date and time of each dose, food consumption status at the time of drug administration.

If a participant misses a dose at the scheduled time, the participant can still take the dose within 4 hours of the scheduled time. If the participant missed taking a dose after 4 hours of the scheduled time, or day of treatment, they must be instructed not to “make it up” but resume subsequent doses as prescribed. This dose will be considered as a missed dose. In addition, if a participant vomits any time after taking a dose, they should not “make it up” but to resume subsequent doses as prescribed. Lastly, if a participant inadvertently takes 1 extra dose during a day, the participant should not take the next dose of PF-07265028.

Food Requirements (Except for the Food-Effect Subset or Cohorts Evaluating Food Intake on Tolerability)

Participants will take PF-07265028 orally with at least 8 oz (240 mL) of water on an empty stomach. No food or liquids other than water will be consumed for 2 hours before and 2 hour following each dose throughout the study).

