6.1.1.2. Sasanlimab (PF-06801591)

For participants in Part 1B and Part 2, qualified and trained investigator site personnel will administer sasanlimab at a fixed dose. See [Section 8.2.7](#) for local site injection tolerability assessment. In the investigational combination therapy with PF-07265028, sasanlimab 300 mg (50 mg/mL), will be administered SC Q4W to the abdomen. Sasanlimab should be administered to 2 or more different quadrants of the abdomen (with preference given to the lower quadrants when possible); 1 or 2 injections per quadrant. If SC injections in the abdominal location are not possible, SC injections can be administered in a distributed manner in the thighs. SC injections in the upper extremities (eg, deltoid, upper and lower arm) are not permitted. Sasanlimab SC injection will be administered at least 30 minutes after administration of PF-07265028. Additional guidance on SC injection site locations is provided in [Appendix 16 Section 10.16](#). For specific instructions on the handling and preparation instructions of study intervention, refer to the Product Specific IP manual. See [Section 8.2.7](#) for local site injection tolerability assessment.

Study staff should refer to the IP manual for specific instructions on the preparation and handling of the study intervention.

A cycle is defined as the time from Day 1 dose to the next Day 1 dose. Participants will receive a single dose of sasanlimab on Day 1 of each cycle.

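### The treatment-duration formula, applied to sasanlimab dosed every 28 days, leaves out the final dosing interval: up to 27 days short per combination participant in the exposure table

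*SAP*

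**What the plan says.** SAP 6.8.3 (Study Treatment Exposure) defines DOT once: "defined as the last active dose date minus the first active dose date + 1". It then adds: "DOT, when it is derived at participant level, will be derived for PF-07265028 and sasanlimab separately". No other formula is offered for sasanlimab. DOT is planned as a continuous summary by dose level or arm. A cycle version (at least 1, 2, 3 cycles and so on) is optional: "DOT may also be categorized into different intervals". The SAP does not say how days become cycles.

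The same section defines compliance, per drug, as cumulative dose taken over cumulative dose planned. It does so once for Cycle 1 and once for the whole treatment period, where the period runs from the first to the last dose given.

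The two drugs have different schedules. PF-07265028 starts as continuous once-daily dosing (Protocol 6.1.1.1). For sasanlimab, Protocol 4.1 says: "In combination therapy, sasanlimab 300 mg SC Q4W will be administered at the clinic together with oral administration of PF-07265028". Protocol 6.1.1.2 says: "Participants will receive a single dose of sasanlimab on Day 1 of each cycle". Protocol 6.5.1 and 6.5.2 rule out sasanlimab dose reductions but allow doses to be delayed or skipped.

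**The concern.** First dose to last dose, plus one day, measures time on a drug taken every day. For a drug given once per 28-day cycle it measures the span between injections and gives no credit for the time covered by the last one. A participant who receives a single sasanlimab injection is recorded as treated for 1 day.

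A reader of the exposure table would see two drugs started together, and continued together for the same number of cycles, with durations almost a cycle apart. Sasanlimab exposure would look shorter than it was. For participants who stop early the difference is most of the figure.

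The overall-compliance window has a related but separate weakness. It always closes on a dose that was given, so doses planned and missed after that point leave the denominator. Because sasanlimab cannot be reduced, omitted or delayed doses are the main way its compliance can fall, and toxicity-driven stopping is what this summary should reveal.

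**Working it through.** **Inputs.** The DOT formula and its separate use for each drug come from SAP 6.8.3. The 28-day sasanlimab interval, one dose per cycle, comes from Protocol 4.1 and 6.1.1.2. The Day 1 window of ±2 days from Cycle 2 comes from Protocol Table 1. Sasanlimab may be held for up to 8 weeks (Protocol 6.5.3). The plan states no exposure figure to reproduce.

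**Continuous DOT.** Let k be the number of sasanlimab doses and D the cumulative delay in days.

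- As written: DOT = 28(k − 1) + 1 + D.
- Through the end of the last dosing interval (last dose + 27 days): 28k + D.
- Difference: 28k + D − [28(k − 1) + 1 + D] = 27 days, whatever k and D are.

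On schedule (D = 0):

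| Doses | DOT as written | Days covered | Shortfall as share of days covered |
|---|---|---|---|
| 1 | 1 | 28 | 27/28 = 96% |
| 2 | 29 | 56 | 27/56 = 48% |
| 3 | 57 | 84 | 27/84 = 32% |
| 6 | 141 | 168 | 27/168 = 16% |

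If death or data cut-off comes t days after the last dose, with t below 27, the shortfall is t days. So 27 is a maximum.

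For PF-07265028 taken daily over k full cycles the formula gives 28k, that is 28, 56 and 84 days, which is right. A participant completing three cycles of the combination would show 84 days of PF-07265028 and 57 days of sasanlimab.

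**Cycle categories.** Assume that at least c cycles means DOT of 28c or more; the SAP does not say this. On schedule, 1, 29, 57 and 85 days then fall in 0, 1, 2 and 3 cycles, one below the number of doses. The exact one-cycle shift holds only for D from −1 to 26:

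- 2 doses, D = 27: 56 days, 2 cycles, no shift.
- 2 doses, D = 56: 85 days, 3 cycles, one high.
- 2 doses, D = −2: 27 days, 0 cycles, two low.

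If started cycles are counted instead (days divided by 28, rounded up), 1, 29, 57 and 85 days give 1, 2, 3 and 4 cycles and the on-schedule shift disappears.

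**Compliance.** Assume a participant dosed in Cycles 1 to 3, held in Cycles 4 and 5, then discontinued from sasanlimab. As written, the window ends at the Cycle 3 dose: 3/3 = 100%. To discontinuation: 3/5 = 60%. If one dose is skipped and a later one given, the skipped dose stays in the planned total under either rule.

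**Who is affected.** About 30 participants in Part 1B and up to 4 × 40 = 160 in Part 2A, as planned numbers (SAP 5.1).

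**The case against.** A reader might infer that every combination participant is placed one cycle too low. The documents do not support that. Only the sasanlimab DOT is affected, and the same participant's PF-07265028 DOT is correct. The cycle categories are optional and have no conversion rule, and a started-cycle rule removes the on-schedule shift. Delays and visit windows make the error zero, one high or two low for some participants even under days/28.

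A reader might also infer that the safety conclusions depend on this table. They do not, as planned. AE summaries are participant counts with no exposure adjustment, and the on-treatment period in SAP 6.1.2 runs to 28 days after the last dose unless new anti-cancer therapy starts. Events in the final interval are therefore already counted. DLT evaluability uses the amount of drug received (Protocol 4.3.3). No DLT, AE-incidence or efficacy analysis uses DOT.

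On compliance, it is fair to say that this is not the same flaw. A window ending at the last dose is not peculiar to 4-weekly dosing and applies to PF-07265028 too. Only omissions after the last given dose drop out. Cycle 1 compliance, which feeds the per-protocol population, has its own window. The participant listing shows planned and actual totals, and sasanlimab is a fixed 300 mg, so doses received can be worked out from it.

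Finally, first-to-last-dose span is a clear and reproducible definition, so this is a choice of convention rather than an arithmetic mistake. That stands as far as it goes. But the continuous summary is a firm plan, nothing elsewhere in either document adds the dosing interval, and a listing does not correct a summary table.

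**Conclusion.** The point holds for sasanlimab and for the descriptive exposure table only. The planned continuous sasanlimab DOT omits the final dosing interval. It is 27 days short where that interval runs its course, and by less where death or cut-off truncates it. This needs no assumption about cycle categories or about earlier delays; it rests only on counting each injection as covering 28 days.

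Two further effects are conditional. The one-cycle shift requires the optional categories to be produced, a days/28 rule, and roughly on-schedule dosing. The compliance overstatement requires doses omitted after the last one given, and the 100% against 60% comparison is an assumed course, not an expected rate. This is a minor but worthwhile correction.

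**What to change.** In SAP 6.8.3:

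- For sasanlimab, define DOT = min(last dose date + 27, death date, data cut-off) − first dose date + 1. On schedule and without truncation this gives 28, 56, 84 and 112 days for 1, 2, 3 and 4 doses. Keep the existing formula for PF-07265028.
- Report the number of sasanlimab doses received and state the days-to-cycles rule. The longer DOT does not remove the need for a rule: two doses with the second given 2 days early would be 26 + 28 = 54 days, still below 2 × 28 = 56.
- Say which definition of a cycle the table uses, since Protocol 6.1.1.1 has "A cycle is defined as 28 days, regardless of missed doses or dose delays" and Protocol 6.1.1.2 has "A cycle is defined as the time from Day 1 dose to the next Day 1 dose".
- End the overall sasanlimab compliance denominator at the sasanlimab discontinuation date, and say whether the PF-07265028 window stays as it is. Leave Cycle 1 compliance unchanged.

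The cost is a wording change and one extra derivation. Protocol 6.4 already has intervention start and stop dates recorded in the CRF. Compliance figures will look slightly less favourable where participants stopped after omitted doses.

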7. INTERIM ANALYSES

No formal interim analysis will be conducted for this study. As this is an open label study, the sponsor may conduct unblinded reviews of the data during the course of the study for the purpose of safety assessment, facilitating dose escalation decisions, facilitating PK/PD modeling, and/or supporting clinical development.

9. APPENDICES

9.1. Appendix 1: Categorical Classes for ECG and Vital Signs

Clinically Relevant Categories for QTcF

QTcF (msec)	max. ≤ 450	$450 < \text{max.} \leq 480$	$480 < \text{max.} \leq 500$	max. > 500
QTcF (msec) increase from baseline	$30 \leq \text{max.} < 60$	max. ≥ 60		

Clinically Relevant Categories for Pulse Rate and QRS

Pulse Rate (msec)	max. ≥ 300	
Pulse Rate (msec) increase from baseline	Baseline > 200 and max. $\geq 25\%$ increase	Baseline ≤ 200 and max. $\geq 50\%$ increase
QRS (msec)	max. ≥ 200	
QRS (msec) increase from baseline	Baseline > 100 and max. $\geq 25\%$ increase	Baseline ≤ 100 and max. $\geq 50\%$ increase

Clinically Relevant Categories for Vital Signs

Systolic BP (mm Hg)	min. < 90	≥ 160 max.
Systolic BP (mm Hg) change from baseline	max. decrease ≥ 30	max. increase ≥ 30
Diastolic BP (mm Hg)	min. < 50	≥ 100 max.
Diastolic BP (mm Hg) change from baseline	max. decrease ≥ 20	max. increase ≥ 20
Supine pulse rate (bpm)	min. < 40	max. > 120

Measurements that fulfil these criteria are to be listed in the study report.
